6.9.1. Primary Outcome and Methodology

The primary outcome is the proportion of patients achieving ASAS40 at Week 16 (Visit 8) in bDMARD-naïve patients. The primary outcome related to improvement in symptomatic feature of AxSpA are assessed at Week 16 (Visit 8) prior to placebo patients being switched to ixekizumab during Period 3 (Extended Treatment Period).

The primary analysis will be based on the ITT Population in bDMARD-naïve patients for the Blinded Treatment Dosing Period (Period 2) comparing the ixekizumab treatment group and placebo at Week 16 (Visit 8). The primary analysis is a logistic regression analysis with treatment and baseline CRP status in the model (Section 6.1.1).

Table RHCH.6.4 provides the detailed analyses including analysis type, method and imputation, population, time point, and treatment comparisons for primary outcome.

6.9.2. Major Secondary Efficacy Analyses

The major secondary outcomes at Week 16 (Visit 8) are:

- Proportion of patients achieving an ASAS40 response in overall population
- Proportion of patients achieving an ASAS20 response in overall population
- Change from baseline in ASDAS in overall population
- Change from baseline in BASDAI in overall population
- Change from baseline in BASFI in overall population
- Proportion of patients achieving ASDAS < 2.1 in overall population
- Change from baseline in MRI SPARCC spine score in overall population
- Change from baseline in SF-36 PCS in overall population*

* Detailed descriptions and analyses on SF-36 PCS are described in Table RHCH.6.5 and Table RHCH.6.6.

The major secondary analysis will be based on the ITT Population for Period 2 comparing the ixekizumab treatment group and placebo at Week 16 (Visit 8).

The primary analysis for categorical major secondary outcomes is a logistic regression analysis with treatment, baseline CRP status and TNF inhibitor experience in the model (only in overall population, Section 6.1.1). Missing data will be imputed using the NRI method (Section 6.3.1).

The primary analysis for continuous major secondary outcomes (except MRI SPARCC spine score) is an MMRM analysis with treatment, baseline CRP status, TNF inhibitor experience, baseline value, visit, baseline value-by-visit, and treatment-by-visit interaction as fixed factors (Section 6.1.1).

The primary analysis for change from baseline in MRI SPARCC spine score is an observed case analysis using ANCOVA with treatment, baseline CRP status, TNF inhibitor experience, and baseline value in the model (Section 6.1.1). Only patients with both baseline and Week 16 SPARCC spine score will be included in the analysis.

These major secondary comparisons will be tested based on the graphical multiple testing procedure detailed in Section 6.4.

Table RHCH.6.4 provides the detailed analyses including analysis type, method and imputation, population, time point, and treatment comparisons for major secondary outcomes.

6.9.3. Additional Analyses of the Primary Outcome

There will be no adjustment for multiple comparisons for additional analyses of the primary outcome, ASAS40.

To support the primary outcome analysis, ASAS40 will be analyzed based on the PPS Population in bDMARD-naïve and overall patients for Period 2 at Week 16 (Visit 8) using a logistic regression analysis with treatment, baseline CRP status, and TNF inhibitor experienced or naïve (only in overall patients) in the model (Section 6.1.1). Missing data will be imputed using the NRI method (Section 6.3.1).

Figures showing the proportion of patients achieving an ASAS40 response at each scheduled visit during Period 2 within each treatment group will be provided.

Time to first ASAS40 response will be assessed based on the ITT Population during Period 2 as described in Section 6.1.1.

Please see Table RHCH.6.4 for details of the additional analyses on primary outcome.

6.9.4. Other Secondary Efficacy Analyses

There will be no adjustment for multiple comparisons for other secondary efficacy analyses.

The other secondary efficacy variables for secondary objectives will be done on:

- ASAS40, ASAS20, ASAS5/6 and partial remission, BASDAI50
- ASDAS inactive disease, ASDAS<2.1, clinically important improvement and major improvement
- Change from baseline in:
 - individual components of the ASAS criteria (patient global, spinal pain, function, inflammation, CRP, and spinal mobility [lateral spinal flexion])
 - BASDAI and inflammation (mean of Q5 and Q6 on BASDAI)
 - ASDAS, BASFI, CRP
 - mobility (BASMI linear and individual components, chest expansion, occiput to wall distance)
 - MRI SPARCC spine score; MRI SPARCC SIJ structural score (SSS) for each of the 4 features: fat metaplasia, bone erosion, backfill and ankyloses; MRI SPARCC SIJ score; enthesitis score (MASES)
 - ASAS-NSAID score (apply to Period 3 analysis only, Section 6.9.4.1)

Treatment comparisons of ixekizumab treatment group and placebo at Week 16 (Visit 8) and all other postbaseline visits during Period 2 will be provided.

Descriptive statistics (that is, no inferential testing) will be provided during Period 3, or Combined Periods 2 and 3, as applicable.

Table RHCH.6.4 provides the detailed analyses including analysis type, method and imputation, population, time point, and treatment comparisons for other secondary outcomes.

6.9.4.1. Analyses on NSAID Intake

ASAS-NSAID score is used to present the NSAID (including COX-2 inhibitor) intake by considering the type of NSAID, the total daily dose, and the number of days on which NSAID has been taken during a period of interest (Dougados et al. 2011). Appendix 2 provides the equivalent dose of each NSAID compared to 150 mg diclofenac (Dougados et al. 2011), additional equivalent scores are listed below:

For the NSAID equivalent scoring system, 0 = no intake, 100 = 150 mg diclofenac, 1000 mg naproxen, 200 mg aceclofenac, 400 mg celecoxib, 600 mg etodolac, 90 mg etoricoxib, 200 mg flurbiprofen, 2400 mg ibuprofen, 150 mg indometacin, 200 mg ketoprofen, 15 mg meloxicam, 200 mg nimesulide, 400 mg phenylbutazone, 20 mg piroxicam, 20 mg tenoxicam (Dougados et al. 2011). Additionally, 100 = 180 mg acemetacin, 3600 mg acetylsalicylic acid, 3600 mg salicylic acid, 32 mg lornoxicam, 360 mg loxoprofen, 1000 mg mefenamic acid, 2000 mg nabumetone, 1000 mg niflumic acid, 600 mg tiaprofenic acid, 90 mg pelubiprofen, 240 mg zaltoprofen, 120 mg ketorolac tromethamine (if used intramuscularly [IM] or intravenous [IV]), 40 mg ketorolac tromethamine (if used orally), 120 mg ketorolac (if used intramuscularly [IM] or intravenous [IV]), 40 mg ketorolac (if used orally), 400 mg sulindac, 1200 mg dexibuprofen, 75 mg dexketoprofen, 1110 mg talniflumate. For Vimovo, esomeprazole strontium w/naproxen, esomeprazole w/naproxen and naproxen w/omeprazole, use the score for naproxen; for caffeine with ibuprofen, CAROL-F, and famotidine w/ibuprofen, use the score for ibuprofen; for Dioxaflex Protec and Arthrotec, use the score for diclofenac; for anacin/00141001/, use the score for acetylsalicylic acid; for paynocil, use the score for salicylic acid.

The general formula for calculating ASAS-NSAID score is:

(equivalent NSAID score) x (days of intake during period of interest) x (days per week)/(period of interest in days).

A score is assigned depending on the frequency of NSAID use per week (Dougados et al. 2011): 7/7: everyday use; 6/7: >5 days/week; 4/7: >3 to ≤5 days/week; 2/7: >1 to ≤3 days/week; 0.5/7: ≤1 day/week; 0: no intake.

For example (Dougados et al. 2011), if during a period of interest (between two visits) of 6 months, if the patient has taken piroxicam 20 mg during the first 4 months on 3-5 days per week and has used 10 mg piroxicam during the remaining 2 months on 2 days a week, the ASAS-NSAID score for the first 4 months is:

$100 (20 \text{ mg piroxicam score}) \times 120 (4 \text{ months}) \times 4/7 (3-5 \text{ days/ week})/180 (6 \text{ months}) = 38.1$

the ASAS-NSAID score for the remaining 2 months is:

$50 (10 \text{ mg piroxicam score}) \times 60 (2 \text{ months}) \times 2/7 (2-3 \text{ days/week})/180 (6 \text{ months}) = 4.8$

The total score for the 6 month period is 42.9 (38.1 plus 4.8).

ASAS-NSAID score will be summarized for the following endpoints at baseline Week 0 (when applicable) and each scheduled visit of interest, which includes the timeframe after the date of previous visit to the date of current visit:

- Change from baseline in ASAS-NSAID
- ASAS-NSAID50, ASAS-NSAID 10, ASAS-NSAID 0.

In addition, proportion of patients taking NSAID at specified visit will be summarized.

6.9.5. Sensitivity Analyses

6.9.5.1. Multiple Imputation

The primary and key categorical secondary endpoints at Week 16 (Visit 8) may be analyzed based on the ITT Population and ITT Population in bDMARD-naïve patients using the multiple imputation (MI) method, as described in Section 6.3.3. Analyses for categorical endpoints will be based on the logistic regression analysis with include treatment, baseline CRP status and TNF inhibitors experience in the model (Section 6.1.1).

6.9.6. Additional Exploratory Analyses

Exploratory analyses like including additional covariates (e.g. pooled sites) in the logistic regression, MMRM or categorical MMRM analysis may be explored. Potential protocol deviations that might have impact on treatment effect including but not limited to the ones in IPD list may also be considered for further excluding from PPS for sensitivity analysis.

6.9.7. Health Outcomes/Quality-of-Life Analyses

The health outcomes and quality of life (QOL) measures are ASAS-HI, SF-36, FACTT-Fatigue, WPAI-SpA and EQ-5D-5L.

The analyses of health outcomes and QOL measures for Period 2 will be based on the ITT Population. Descriptive statistics will be provided for Period 3 based on the Extended Treatment Period Population.

[Table RHCH.6.5](#) includes the description and derivation of the health outcomes and QOL measures.

[Table RHCH.6.6](#) provides the detailed analyses including analysis type, method and imputation, population, time point, and treatment group comparisons for health outcomes and QOL analyses.

Table RHCH.6.5. Description and Derivation of Health Outcomes and Quality-of-Life Measures

Measure / Description	Variable	Derivation / Comment	Imputation Approach if with Missing Components

ASAS Health Index:
 
The ASAS-Health Index (ASAS-HI) is a disease specific health-index instrument designed to assess the impact of interventions for SpA, including axSpA. The 17 item instrument has scores ranging from 0 (good Health) to 17 (poor Health) (Kiltz et al. 2013). Each item consists of 1 question that the patient needs to respond to with either “I agree” (score 1) or “I do not agree (score 0).” A score of “1” is given where the item is affirmed, indicating adverse health.
	ASAS-HI	
All item scores are summed to give a total score or index. Range: 0 to 17 0 (good health) and 17 (poor health) Note, items # 7 and #8 may not be applicable for some patients. For those patients who ticked the response “not applicable”, the sum score is analyzed based on n=16 or n=15, respectively.
	
If ≥ 4 items ($>20\%$) have missing response, then ASAS-HI is missing. If <4 items ($\leq 20\%$) missing, then imputed sum = sum of scores from nonmissing items $\times n / (n - \text{no. of missing items})$, where n is the total number of applicable items, e.g. 15, 16, or 17. [ASAS Health Index User Manual (WWW)].


Medical Outcomes Study 36-item Short-Form Health Survey:
 
The SF-36 is a 36-item patient-administered measure designed to be a short, multipurpose assessment of health in the areas of physical functioning, role – physical, role – emotional, bodily pain, vitality, social functioning, mental health, and general health. The 2 overarching domains of mental well-being and physical well-being are captured by the Mental Component Summary and Physical Component Summary scores. The summary scores range from 0 to 100; higher scores indicate better levels of function and/or better health. Items are answered on Likert scales of varying lengths. The SF-36 version 2 (acute version) will be used, which utilizes a 1-week recall period (Ware [2000]).
	
8 associated domain scores:
 
 • Physical Functioning, • Role Physical, • Bodily Pain, • General Health, • Vitality, • Social Functioning, • Role Emotional, • Mental Health 
2 component Scores:
 
 • MCS Score • PCS Score 
PCS change from baseline – Major Secondary
	
Per copyright owner, the Quality Metric Health Outcomes™ Scoring Software will be used to derive SF-36 domain and component scores. After data quality-controls, the SF-36 software will re-calibrate the item-level responses for calculation of the domain and component scores. These raw scores will be transformed into the domain scores (t-scores) using the 1-week recall period. The summary scores range from 0 to 100.
	
If an item is missing, there will be imputation conducted by the Scoring Software.

Measure / Description	Variable	Derivation / Comment	Imputation Approach if with Missing Components

Functional Assessment of Clinical Illness Therapy Fatigue (FACIT-Fatigue) Scale:
 
The FACIT-Fatigue scale (Cella and Webster 1997) is a 13-item symptom-specific questionnaire that assesses the self-reported severity of fatigue and its impact upon daily activities and functioning.
	
FACIT-Fatigue total score
	
The FACIT-Fatigue uses 0 (“not at all”) to 4 (“very much”) numeric rating scales to assess fatigue and its impact in the past 7 days. Scores range from 0 to 52 with higher scores indicating less fatigue. The FACIT-Fatigue Scoring Guidelines (Version 4) will be used to calculate the Total Score. Reversals are needed for all items except An5 and An7, as described in scoring manual. http://www.ser.es/wp-content/uploads/2015/03/FACIT-F_INDICE.pdf
	
Missing items are acceptable as long as more than 50% of the items are answered (i.e., a minimum of 7 out of 13 items), the sum of available items will be divided by the number of items answered to obtain the total score. If less than 7 items are answered, the FACIT-Fatigue total score will be set to missing.

Work Productivity and Activity Impairment Questionnaire—Spondyloarthritis:
 
The Work Productivity and Activity Impairment—Spondyloarthritis (WPAI-SpA) consists of 6 questions to determine employment status, hours missed from work because of spondyloarthritis, hours missed from work for other reasons, hours actually worked, the degree to which spondyloarthritis affected work productivity while at work, and the degree to which spondyloarthritis affected activities outside of work. The WPAI-SpA has been validated in the AS patient population (Reilly et al. 2010). Four scores are derived: percentage of absenteeism, percentage of presenteeism (reduced productivity while at work), an overall work impairment score that combines absenteeism and presenteeism, and percentage of impairment in activities performed outside of work. Greater scores indicate greater impairment.
	
percentage of absenteeism
	
% work time missed due to problem: $(Q2/(Q2 + Q4))*100$
	
if Q2 or Q4 is missing, then missing

	
percentage of presenteeism
	
% impairment while working due to problem: $(Q5/10)*100$
	
if Q5 is missing, then missing

	
overall work impairment score
	
% overall work impairment due to problem: $(Q2/(Q2+ Q4) + [(1-Q2/(Q2+Q4))*(Q5/10)])*100$
	
if any of Q2, Q4, or Q5 is missing, then missing

	
percentage of impairment
	
% activity impairment due to problem: $(Q6/10)*100$
	
if Q6 is missing, then missing

Measure / Description	Variable	Derivation / Comment	Imputation Approach if with Missing Components

European Quality of Life – 5 Dimensions 5 Level:
 
EQ-5D-5L: is a standardized measure of health status used to provide a simple, generic measure of health for clinical and economic appraisal. The EQ-5D-5L consists of 2 components: a descriptive system of the respondent's health and a rating of his/her current health state using a 0- to 100-mm VAS. The descriptive system comprises the following 5 dimensions:
 
 item 1: mobility item 2: self-care item 3: usual activities item 4: pain/discomfort item 5: anxiety/depression 
The respondent is asked to indicate his/her health state by ticking (or placing a cross) in the box associated with the most appropriate statement in each of the 5 dimensions.
 
The VAS records the respondent's self-rated health on a vertical VAS where the endpoints are labeled 100 = "best imaginable health state" and 0 = "worst imaginable health state".
	
EQ-5D mobility EQ-5D self-care EQ-5D usual activities EQ-5D pain/discomfort EQ-5D anxiety/depression
	
Five health profile dimensions, each dimension has 5 levels:
 
 1 = no problems 2 = slight problems 3 = moderate problems 4 = severe problems 5 = extreme problems 
It should be noted that the numerals 1 to 5 have no arithmetic properties and should not be used as a primary score
	
Each dimension is a single item, missing if missing

	
EQ-5D-5L UK Population based index score
	
Derive EQ-5D-5L UK Population-based index score according to the link by using the UK algorithm (Szende et al. 2007) to produce a patient-level index score between -0.59 and 1.0 (continuous variable): https://euroqol.org/wp-content/uploads/2018/02/EQ-5D-5L_Crosswalk_Value_Sets.xls
	
If any of the items is missing, the index score is missing

	
EQ-5D-5L Chinese Population based index score
	
Derive EQ-5D-5L Chinese Population-based index score (Luo et al. 2017) to produce a patient-level index score between 0 and 1: https://ars.els-cdn.com/content/image/1-s2.0-S1098301516341250-mmc1.xls
	
If any of the items is missing, the index score is missing

	
EQ-5D VAS
	
Range from 0 = "worst imaginable health state" to 100 = "best imaginable health state". Note: higher value indicates better health state.
	
Single item, missing if missing

Abbreviations: ASAS = Assessment of Spondyloarthritis International Society; MCS = mental component summary; NRS = numeric rating scale; PCS = physical component summary.

Table RHCH.6.6. Description of Health Outcomes and Quality-of-Life Analyses

Measure	Variable	Analysis Method (Sections 6.1 and 6.3)	Population (Section 6.1.5)	Comparison/Time Point	Analysis Type
36 item Short Form Health Survey (SF-36)	PCS change from baseline Major Secondary	MMRM; ANCOVA with mBOCF	ITT Population	IXE80Q4W vs. placebo at Week 16 and all other postbaseline visits in Period 2	Major secondary analysis is MMRM analysis for ITT Population comparing IXE80Q4W vs. placebo at Week 16 (Section 6.9.2). Health Outcomes/QOL analyses (Section 6.9.7).
		Descriptive statistics of change from baseline	Extended Treatment Period Population	No comparison during Period 3	Health Outcomes/QOL analyses (Section 6.9.7).
		Descriptive statistics of change from baseline	ITT Population Who are Initially Randomized to Ixekizumab	No comparison during Combined Periods 2 and 3	Health Outcomes/QOL analyses (Section 6.9.7).
	MCS and domain scores change from baseline	MMRM	ITT Population	IXE80Q4W vs. placebo at Week 16 and all other postbaseline visits in Period 2	Health Outcomes/QOL analyses (Section 6.9.7).
		Descriptive statistics of change from baseline	Extended Treatment Period Population	No comparison during Period 3	Health Outcomes/QOL analyses (Section 6.9.7).
	ASAS Health Index (ASAS- HI)	change from baseline	MMRM	ITT Population	IXE80Q4W vs. placebo at Week 16 and all other postbaseline visits in Period 2
Descriptive statistics of change from baseline			Extended Treatment Period Population	No comparison during Period 3	Health Outcomes/QOL analyses (Section 6.9.7).

Measure	Variable	Analysis Method (Sections 6.1 and 6.3)	Population (Section 6.1.5)	Comparison/Time Point	Analysis Type
Functional Assessment of Chronic Illness Therapy (FACIT) Fatigue Scale	change from baseline	MMRM	ITT Population	IXE80Q4W vs. placebo at Week 16 and all other postbaseline visits in Period 2	Health Outcomes/QOL analyses (Section 6.9.7).
		Descriptive statistics	Extended Treatment Period Population	No comparison during Period 3	Health Outcomes/QOL analyses (Section 6.9.7).
Work Productivity and Activity Impairment Questionnaire—Spondyloarthritis	Change from baseline in: 
 percentage of absenteeism percentage of presenteeism overall work impairment score percentage of impairment 	ANCOVA with mBOCF	ITT Population	IXE80Q4W vs. placebo at Week 16 in Period 2	Health Outcomes/QOL analyses (Section 6.9.7).
		Descriptive statistics of change from baseline	Extended Treatment Period Population	No comparison during Period 3	Health Outcomes/QOL analyses (Section 6.9.7).
European Quality of Life – 5 Dimensions 5 Level (EQ-5D-5L)	EQ-5D mobility, EQ-5D self-care, EQ-5D usual activities, EQ-5D pain/discomfort, EQ-5D anxiety/depression	For category “no problem”: Logistic regression with NRI; Fisher’s exact test with NRI	ITT Population	IXE80Q4W vs. placebo at Week 16 in Period 2	Health Outcomes/QOL analyses (Section 6.9.7).
		Descriptive statistics of each category and proportion of patients with “no problems”	Extended Treatment Period Population	No comparison during Period 3	Health Outcomes/QOL analyses (Section 6.9.7).

Measure	Variable	Analysis Method (Sections 6.1 and 6.3)	Population (Section 6.1.5)	Comparison/Time Point	Analysis Type
	Change from baseline in EQ-5D-5L UK EQ-5D-5L Chinese index	ANCOVA with mBOCF	ITT Population	IXE80Q4W vs. placebo at Week 16 in Period 2	Health Outcomes/QOL analyses (Section 6.9.7).
	Population-based index scores, EQ-5D VAS	Descriptive statistics of change from baseline	Extended Treatment Period Population	No comparison during Period 3	Health Outcomes/QOL analyses (Section 6.9.7).

Abbreviations: ANCOVA = analysis of covariance; ASAS = Assessment of Spondyloarthritis International Society; IXE80Q4W = ixekizumab 80 mg every 4 weeks; ITT = intent-to-treat; mBOCF = modified baseline observation carried forward; MCS = mental component summary; MMRM = mixed-effects model of repeated measures; NRI = nonresponder imputation; PCS = physical component summary; QOL = quality of life.

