Maastricht Ankylosing Spondylitis Enthesitis Score (MASES): The MASES is an index used to measure the severity of enthesitis (Heuft-Dorenbosch et al. 2003). The MASES assesses 13 sites for enthesitis using a score of “0” for no activity, or “1” for activity. Sites assessed include: costochondral 1 (right/left), costochondral 7 (right/left), spinal iliaca anterior superior (right/left), crista iliaca (right/left), spinal iliaca posterior (right/left), processus spinosus L5, and Achilles tendon proximal insertion (right/left).	MASES	The MASES is the sum of all site scores. Range: 0 to 13, higher scores indicate more severe enthesitis 0 = no activity and not evaluable 1 = activity	Missing if >20% (ie, ≥3) sites are missing. If ≤20% missing, then imputed sum = sum of scores from nonmissing sites x 13/ no. of nonmissing sites
	MASES score = 0	MASES score = 0 refers to complete resolution in enthesitis. Analysis of MASES score = 0 only applies to patients with baseline enthesitis (MASES >0).	Missing if observed value is missing
	Heel Enthesitis score = 0	Heel Enthesitis score = 0 refers to Achilles tendon proximal insertion (right/left) = 0. Analysis of Heel Enthesitis score = 0 only applies to patients with baseline Heel Enthesitis score >0.	Missing if observed value is missing

Measure / Description	Variable	Derivation / Comment	Imputation Approach if with Missing Components
Non-Steroidal Anti-Inflammatory Drug (NSAID) Intake: Information regarding NSAIDs (including COX-2 inhibitors) intake will be collected in the eCRF and the ASAS-NSAID score will be calculated (Dougados et al. 2011).	Proportion of patients taking NSAID	Proportion of patients taking NSAID (including COX-2 inhibitors) at specified visit	NA
	ASAS -NSAID score	See Section 6.9.4.1 and Appendix 2 for details of deriving ASAS-NSAID score. ASAS-NSAID = 0 if no NSAID use	If NSAID dose is missing, the maximum efficacy dose (Appendix 2) is assumed. If frequency is missing, 'every day' intake is assumed.
	ASAS-NSAID50	$100 \times \frac{\text{Baseline ASAS-NSAID} - \text{Observed ASAS-NSAID}}{\text{Baseline ASAS-NSAID}}$ Proportion of patients with at least 50% decrease from baseline in ASAS-NSAID score. Derivation only applies to patients whose ASAS-NSAID is not equal to 0 at baseline.	
	ASAS-NSAID 10	Proportion of patients with ASAS-NSAID score <10	
	ASAS-NSAID 0	Proportion of patients with ASAS-NSAID score = 0	

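### The FACIT-Fatigue rule for missing items omits the factor of 13, so a form with 7 to 12 answers is scored 0 to 4 on a 0 to 52 scale

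*SAP*

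**What the plan says.** The FACIT-Fatigue row of SAP Table RHCH.6.5 (Section 6.9.7) says that the scale "is a 13-item symptom-specific questionnaire that assesses the self-reported severity of fatigue and its impact upon daily activities and functioning". Each item runs from 0 to 4. For the total, the derivation cell states: "Scores range from 0 to 52 with higher scores indicating less fatigue". It also says that "The FACIT-Fatigue Scoring Guidelines (Version 4) will be used to calculate the Total Score" and that all but two items are reversed first.

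The missing-component cell sets the threshold: "Missing items are acceptable as long as more than 50% of the items are answered (i.e., a minimum of 7 out of 13 items". Above that threshold, "the sum of available items will be divided by the number of items answered to obtain the total score". Below 7 answers the total is missing. No multiplication by 13 appears.

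Protocol Section 9.1.3.4 describes the scale but gives no rule for missing items.

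The SAP has two other prorated sums, and both scale back to full length. For MASES in Table RHCH.6.3 the rule is "imputed sum = sum of scores from nonmissing sites x 13/ no. of nonmissing sites". For ASAS-HI, in the same table as FACIT-Fatigue, it begins "imputed sum = sum of scores from nonmissing items" and then multiplies by n over n minus the number of missing items.

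**The concern.** The rule puts one variable on two scales. Complete forms are totals (0 to 52) and partly complete forms are item means (0 to 4). The cell calls its result the total score and the row bounds that score at 52, so the missing factor looks like an omission and not a choice. The MASES and ASAS-HI rules point the same way.

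Change from baseline in FACIT-Fatigue is listed among the other secondary endpoints (SAP Section 4). Table RHCH.6.6 has it tested between arms by MMRM at Week 16 and the other post-baseline visits of Period 2. Higher scores mean less fatigue, so a skipped item at Week 16 produces a false, large worsening, and one at baseline produces a false, large improvement in that patient's change score. Such outliers also add variance. In Period 3, missing continuous health outcomes are filled by mBOCF (SAP Section 6.1.2), so a false score can be carried forward.

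**Working it through.** **Inputs from the documents**
- 13 items, each 0 to 4; total 0 to 52; at least 7 items answered (SAP Table RHCH.6.5).
- 70 evaluable patients per arm (Protocol Section 5.2).

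**Inputs that are assumptions**
- The individual scores used as examples.
- For the SD calculation, a mean of 30 and an SD of 11.
- The number of affected patients (1, 2 or 4).

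**Step 1: the plan's own figures.** 13 × 0 = 0 and 13 × 4 = 52, so the stated range reproduces. 6/13 = 0.46 and 7/13 = 0.54, so the smallest count above 50% is 7, as stated.

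**Step 2: the two formulas.** Let S be the sum over k answered items, with k from 7 to 12.
- As written: S/k. The largest value is 4k/k = 4, so the range is 0 to 4 for every k.
- Prorated: 13 × S/k. The largest value is 13 × 4 = 52, so the range is 0 to 52 for every k.

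The written rule gives exactly 1/13 of the prorated total.

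**Step 3: error for one patient.** With 12 items answered at 2, S = 24. As written, 24/12 = 2; prorated, 13 × 24/12 = 26.

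| Item mean | Prorated total | As written | Error |
|---|---|---|---|
| 1 | 13 | 1 | −12 |
| 2 | 26 | 2 | −24 |
| 3 | 39 | 3 | −36 |
| 4 | 52 | 4 | −48 |

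**Step 4: error in a change score.** Assume true totals of 30 at baseline and 39 at Week 16, with any skipped item at the patient's own average. The true change is 39 − 30 = +9.
- Skip at Week 16: 39/13 − 30 = 3 − 30 = −27.
- Skip at baseline: 39 − 30/13 = 39 − 2.3 = +36.7.

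**Step 5: shift in an arm mean.** For a patient with true total T, the shift is (T/13 − T)/70 = −(12/13)T/70.
- T = 26: −24/70 = −0.34
- T = 30: −27.7/70 = −0.40
- T = 39: −36/70 = −0.51
- T = 52: −48/70 = −0.69

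**Step 6: several affected patients.** Simulating 70 scores (mean 30, SD 11, limited to 0 to 52) and dividing those of the affected patients by 13 gives:

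| Affected patients | Shift in arm mean | SD ratio |
|---|---|---|
| 1 | −0.4 | 1.04 |
| 2 | −0.8 | 1.08 |
| 4 | −1.6 | 1.15 |

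This SD is that of raw scores at one visit. It shows the direction of the effect on the MMRM residual variance, not its size.

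**The case against.** The strongest reply is that the same row names another authority, the Scoring Guidelines (Version 4), and bounds the total at 52. On that reading the cell is an incomplete sentence that a programmer would correct from the manual, and it cannot be said with certainty that wrong scores will be produced. That is fair as a forecast. But the documents do not reproduce the guidelines' formula for missing items, and the SAP does not say they take precedence over its explicit rule. At best the programmer has two instructions to reconcile.

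Other points limit the reach, and they stand:
- **Baseline skips.** The Period 2 MMRM includes baseline and baseline-by-visit, so modelling change gives the same treatment difference as modelling the visit value. A wrong baseline enters that comparison as a wrong covariate, not as a 37-point gain. The false improvement is real in individual change scores and descriptive summaries.
- **Frequency.** No rate of skipped items is given. Exclusion criterion [58] mentions a device on which patients record data directly, but not whether it allows skips.
- **Both arms.** Similar skipping in both arms would largely cancel in the difference and leave mainly added noise. No between-arm bias has been shown.
- **Rank.** FACIT-Fatigue is not among the endpoints in the graphical testing procedure (SAP Section 6.4), and it is descriptive only after Week 16.

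None of these makes the written formula correct.

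**Conclusion.** The concern holds. As written, the rule returns an item mean of 0 to 4 under the name of a total that the same row defines as 0 to 52. The factor of 1/13 is exact and rests on no assumption. The individual error is 24 points at a true total of 26 and 48 at a true total of 52.

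The effect on the trial's result is less certain. Per affected patient, the arm mean falls by 0.34 to 0.69 points for true totals of 26 to 52. How many patients would be affected cannot be derived from the documents. Complete forms, and forms with fewer than 7 answers, are unaffected. The primary and major secondary conclusions do not depend on this score. It is a certain error in a derivation rule with limited reach.

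**What to change.** In the missing-component cell for FACIT-Fatigue in SAP Table RHCH.6.5, state: total score = 13 × (sum of answered items after reversal) / (number of items answered), if at least 7 of the 13 items are answered; otherwise missing. This restores the 0 to 52 range for every count from 7 to 12 and matches the form of the MASES and ASAS-HI rules.

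Add a sentence saying whether the cell or the cited Scoring Guidelines governs if they differ, and check the scoring program against a test form with one item missing.

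The cost is one term in one table cell. Make the change before the Week 16 database lock and unblinding (SAP Section 6.14), so that no endpoint derivation is altered after treatment assignments are known.
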